1. INTRODUCTION AND RATIONALE

1.1 Background

Primary liver cancer consists predominantly of Hepatocellular Carcinoma (HCC). HCC is the fifth most common cancer in men, seventh in women and the third most common cause of cancer mortality (*de Lope C R, Tremosini S, Forner A, Reig M, Bruix J; Journal of Hepatology*2012;S75–S87). In addition, it is also the leading cause of death in patients with cirrhosis in Europe and the US (*Llovet JM, Burroughs A, Bruix J. Hepatocellular carcinoma. Lancet* 2003;362(9399):1907-17). Many patients diagnosed with HCC will have advanced disease where only palliative care is available to them, contributing to a relatively low reported 5-year survival rate of approximately 10%.

Growing information regarding the molecular mechanisms that induce and maintain hepatocarcinogenesis is important as HCC is rarely found in a background of a healthy liver. Major risk factors that have been linked to the development of HCC include alcohol induced liver disease, chronic Hepatitis C and B virus (HCV and HBV) infections; with cancer risk increasing sharply in response to chronic injury at the cirrhosis stage. Additional epidemiological and pre-clinical studies have also investigated chronic inflammatory conditions at specific organ sites which provide evidence that inflammation promotes malignant transformation.

The production of tumour-promoting cytokines by immune/inflammatory cells can activate transcription factors, such as STAT3 via the JAK/STAT pathway in premalignant cells. Once activated STAT3 drives the expression of multiple genes important for cell activation, localization, survival, and proliferation (Valentino and Pierre 2006). It is therefore hypothesised that the inhibition of JAK may directly affect malignant cell proliferation as well as possibly suppressing some negative effects related to the inflammatory state.

HCC patients have only limited non-surgical treatment options in the UK, with sorafenib and lenvatinib being the only licensed systemic treatments that provide a limited survival benefit. Therefore alternative novel approaches for the treatment of advanced HCC represents a high unmet medical need.

1.2 Itacitinib

Itacitinib is a small molecule inhibitor with selectivity for Janus Kinase 1 (JAK1) that is proposed for development for the treatment of myelofibrosis (MF), rheumatoid arthritis (RA), psoriasis, graft-versus- host-disease (GVHD), solid tumours, and B-cell malignancies. Members of the JAK family (JAK1, JAK2, JAK3, and TYK2) play an important role in signal transduction transmitting extracellular ligand binding into an intracellular response following the binding of cytokine and growth factor to their receptors.

JAKs are activated through a process of autophosphorylation enabling them to phosphorylate specific tyrosine residues on the cytokine receptors that serve as docking sites for multiple proteins, including latent STATs. The receptor-associated STATs (and other substrates) can then be phosphorylated by JAKs, resulting in their activation. Once activated STATs become transcription factors and drive the expression of multiple genes important for cell activation, localization, survival, and proliferation (Valentino and Pierre 2006).

1.2.1 Inhibition of JAKS as a target for Solid Tumours

In contrast to normal cells STATs (particularly STAT3) are persistently phosphorylated in most malignancies (Sansone and Bromberg 2012). The persistent or constitutive phosphorylation of STAT3 in cancers may occur via a variety of mechanisms, including increased expression of cytokines and cytokine receptors, decreased expression of the negative regulatory proteins such as suppressor of cytokine signalling (SOCS) through promoter methylation, and loss of tyrosine phosphatases that dephosphorylate JAKs and STATs.

Neoplastic progression involves JAK/STAT pathway activity through cell autonomous and non-cell autonomous mechanisms. Cell autonomous mechanisms refer to intrinsic alterations to the tumour cell that allow them to develop abnormal properties. The presence of STAT3 allows the cell the ability to sustain cell proliferation and block apoptosis (Lesina et al 2011); mediate cell cycle progression during oncogenic stress (Toyonaga et al 2003, Thoennissen et al 2009); control invasiveness, metastasis, and angiogenesis; and confer chemotherapeutic resistance (Catlett-Falcone et al 1999) as major mechanisms contributing to cancer. Non-cell autonomous mechanisms refer to the extrinsic effects mediated by tumour microenvironment, stroma, immune system, and stellate cells (Masamune et al 2005); these have been shown to play an integral role in pancreatic neoplasia and are substantially shaped to a great extent by JAK/STAT signalling.

In addition, JAK/STAT-dependent inflammatory cytokines such as IL-6 and IFN- γ are critical mediators of cancer cachexia, a significant cause for cancer morbidity and mortality. Based on this evidence, it is hypothesized that inhibition of JAKs may directly affect malignant cell proliferation and may suppress the inflammatory state leading to improvements in nutritional status, fatigue, tolerance to therapy, and prolonged survival in patients with advanced cancers that are driven by these intrinsic and extrinsic pathways influenced by STATs. This hypothesis is supported by evidence that JAK/STAT inhibitors are able to slow tumour cell growth and prolong survival in *in vivo* models (Thoennissen et al 2009, Toyonaga et al 2003, Iwanski et al 2010).

Further details can be found in the investigator brochure.

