1.2.2 Pre-Clinical Studies

1.2.2.1 In Vitro Studies

The selective inhibition of JAK1 compared to JAK2 by Itacitinib has been demonstrated in biochemical assays; with additional analyses performed using cell-based assays known to signal through JAK2 homodimer (Murray 2007).

Effects of pathogenesis of RA, such as IL-2 stimulated phosphorylation of JAKs and STATs and IL-2- induced proliferation of cells; as well as the inhibition of phosphorylation of STAT proteins and the production of proinflammatory factors (eg, IL-17, MCP-1) induced by other cytokines, such as IL-23 and IL-6 have also been seen with ICNB039110.

Analysis of human INA-6 multiple myeloma cell line determined the ability of Itacitinib to inhibit cell growth by the inactivation of JAK/STAT3 through the withdrawal of IL-6 or inhibition of IL-6 binding to the IL-6 receptor which induces cell death via apoptosis (Burger et al 2001).

Whole blood assays were used to estimate the effectiveness of blocking JAK in hematopoietic cells *in vivo*, results showed Itacitinib blocked IL-6- induced STAT3 phosphorylation in human whole blood, whereas the potency of Itacitinib in blocking TPO-induced pSTAT3 was significantly reduced, consistent with the JAK1 selectivity measured in the biochemical assays.

Further details can be found in the investigator brochure.

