1.3 Rationale

The aim of the study is to assess the effects of the JAK1 inhibitor Itacitinib as a second line treatment on patients with advanced inflammatory HCC. Inflammatory cells have been seen to produce cytokines that can activate STAT3 via the JAK pathway. This in turn enables them to become transcription factors and drive the expression of multiple genes important for cell activation, localisation, survival, and proliferation. It is therefore hypothesised that the ability of Itacitinib to inhibit the JAK pathway may cause a positive response in the patient's tumour.

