2.3 Translational / Exploratory Objectives and Endpoints

| Objective | Endpoint |
|--|---|
| 1. To assess for presence of predefined JAK1 mutations in tumour tissue and correlate with treatment outcome | To assess for presence of predefined JAK1 mutations in tumour tissue (NGS) and correlate with treatment outcome (mRECIST) |
| 1. To assess for presence of predefined JAK1 mutations in ctDNA | To assess for presence of predefined JAK1 mutations in ctDNA (NGS) |
| 1. To correlate changes in pro-inflammatory cytokines with treatment response | To correlate changes in pro-inflammatory cytokines (multiplex cytokine bead array) with treatment response (mRECIST) |

[figure not shown]

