3.4 Procedures and Measurements

3.4.1 Visit Schedule

Patients will be seen at screening then on day 1 and day 7 of cycle 1 and then every 4 weeks (from date of day 1) in clinic whilst on treatment. Treatment will continue until disease progression. When the patients stops treatment they will be required to attend a safety follow-up visit 28 days of treatment completion. For assessment details see table 1.

Table 1: Scheduled assessments

| Time point → Assessment ↓ | Screening | Cycle 1 | | Cycle 2 | Cycle 3 | Cycle 4 | Cycle 5 | Cycle 6 - Onwards | End of Treatment ¹⁰ | Safety Follow-up |
|---|-----------------|-----------------|-----------------|---------|---------|---------|---------|-------------------------------|-----------------------------------|--------------------------------|
| | Day -28 to 0 | Day 1 Week 1 | Day 7 Week 1 | Week 4 | Week 8 | Week 12 | Week 16 | Week 20 – Every 4 Weeks | | 28 days after last dose. |
| Informed Consent | X | | | | | | | | | |
| Medical History | X | | | | | | | | | |
| Demographics | X | | | | | | | | | |
| Height | X | | | | | | | | | |
| Vital Signs ¹ | X | X | X | X | X | X | X | X | X | X |
| Physical Exam | X | X | X | X | X | X | X | X | X | X |
| ECOG Performance Status | X | X | X | X | X | X | X | X | X | X |
| ECG ⁶ | X | | | | x | | | X ⁷ | | |
| Pregnancy Test | X ¹¹ | | | X | X | X | X | X | | |
| Haematology ² | X | X | X | X | X | X | X | X | X | X |
| Biochemistry ³ | X | X | X | X | X | X | X | X | X | X |
| Serology ⁴ | X | | | | | | | | | |
| Tumour Assessments (mRECIST) ⁵ | X | | | | X | | | X ⁵ | X ⁹ | |
| Archival Tissue or Fresh Frozen Research Biopsy – Mandatory | X | | | | | | | | | |
| Research Bloods ⁸ | X | | | | X | | | X ⁸ | X | |
| ctDNA sample ⁸ | X | | | | X | | | X ⁸ | X | |
| PK Sample ⁶ | | | X | | | | | | | |
| Itacitinib administration | | X | | X | X | X | X | X | | |
| Adverse Events | | X | | | | | | | | |
| Concomitant Medications | | X | | | | | | | | |

- Vital signs include weight, blood pressure, pulse, temperature
- Haematology includes: white blood cell count (WBC) with differential, haemoglobin (Hgb), haematocrit (Hct), and platelet count
- Biochemistry includes: Chem 7 (sodium [Na], potassium [K] chloride [Cl], bicarbonate [CO₂], blood urea nitrogen [BUN], creatinine [Cr], glucose), liver function tests (LFTs - ALT, AST, alkaline phosphatase, total bilirubin, direct bilirubin), LDH, total protein, calcium, phosphate, magnesium, and cholesterol.

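### Section 2.3 relates only the change in cytokines to response: adjust that analysis for the screening level, and name screening inflammation as an exploratory marker

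*Combined protocol and SAP*

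**What the plan says.** All references are to the combined protocol and SAP.

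- **Aim.** Section 1.3 describes itacitinib as a "second line treatment on patients with advanced inflammatory HCC". Section 1.2.1 hypothesises direct effects on tumour cells and suppression of inflammation, leading among other things to "prolonged survival in patients with advanced cancers that are driven by these intrinsic and extrinsic pathways influenced by STATs".
- **Entry.** Sections 3.3.1 and 3.3.2 contain no criterion based on inflammation or pathway activity.
- **Biomarker endpoints (section 2.3).** There are three: "To assess for presence of predefined JAK1 mutations in tumour tissue (NGS) and correlate with treatment outcome (mRECIST"; "To assess for presence of predefined JAK1 mutations in ctDNA (NGS", which has no link to outcome; and "To correlate changes in pro-inflammatory cytokines (multiplex cytokine bead array) with treatment response (mRECIST". The third is the only one that concerns inflammation, and it uses change alone.
- **Material collected (section 3.4.1, Table 1).** Research bloods are marked at screening, week 8, every 8 weeks afterwards and end of treatment. Screening haematology gives a differential: "Haematology includes: white blood cell count (WBC) with differential".
- **Analysis (section 7.2.1).** Translational endpoints get descriptive measures and univariate models. A general clause adds univariate models for demographic and other study variables, and 95% confidence intervals for all estimates. Section 7.2 defers further detail to a separate SAP, which is not among the documents.

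**The concern.** Being an inflammatory HCC is a property of the patient before treatment. Entry does not select for it, so inflammatory state will vary among the 25 patients, and the natural exploratory question is whether outcome varies with the screening level. No named analysis asks this.

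The analysis that is named answers a different question, and answers it with contamination. A patient who starts high has more room to fall, so change carries information about the starting level. If the starting level relates to outcome for any reason, prognostic or otherwise, an unadjusted correlation of change with response picks that up and can be read as a drug-mediated effect. It can also hide a real on-treatment relation. In addition, section 1.2.2.1 reports that the drug inhibits in vitro "the production of proinflammatory factors (eg, IL-17, MCP-1) induced by other cytokines". A fall on treatment may therefore partly be a direct drug effect, which is another reason not to let change stand in for inflammatory state before treatment.

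At stake is the interpretation of one exploratory result, not a primary or secondary endpoint.

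**Working it through.** **Inputs from the plan (section 7.1).** N = 25; stage 1 has 15 patients and stops at 0 responses; success is at least 4 of 25; response rates 5% and 25%.

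**Assumed inputs (not in the documents).** Equal variance of screening and on-treatment cytokine level; within-patient correlation ρ = 0.4, 0.6 or 0.8; screening level correlated 0.5 with a continuous outcome; two-sided 5% test.

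**1. The plan's own figure.** Rejection probability = Σ over x = 1 to 15 of P(X₁ = x; 15, p) × P(X₂ ≥ 4 − x; 10, p).
- p = 0.25: 0.9008, so the stated power of 0.90 reproduces.
- p = 0.05: 0.0336, within the nominal 0.05.
- Early stop: 0.95¹⁵ = 0.463 at 5%; 0.75¹⁵ = 0.013 at 25%.

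Nothing proposed below alters these.

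**2. Change is tied to baseline.** Let B be the screening value and P the later value, each with variance 1 and correlation ρ, and let C = P − B. Then Cov(B, C) = ρ − 1 and Var(C) = 2(1 − ρ), so corr(B, C) = −√((1 − ρ)/2).

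**3. Association when change adds nothing.** If outcome Y depends on B only, with r = 0.5, then corr(Y, C) = 0.5 × corr(B, C). By the Fisher z approximation, the test statistic is centred at atanh(|corr(Y, C)|) × √(25 − 3).

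| ρ | corr(B, C) | corr(Y, C) | centre of z | P(significant) |
|---|---|---|---|---|
| 0.4 | −0.548 | −0.274 | 1.318 | 0.261 |
| 0.6 | −0.447 | −0.224 | 1.067 | 0.187 |
| 0.8 | −0.316 | −0.158 | 0.748 | 0.116 |

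Simulation of this setting at n = 25 gives about 13% to 28% unadjusted and about 4% to 6% once the screening value is in the model. The distortion exists only if baseline matters: with r = 0 the unadjusted test keeps its 5%. Reducing the outcome to response yes/no weakens the correlation, so the excess would then be smaller.

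**4. The opposite error.** With standardised coefficients, corr(Y, C) = β_C + β_B × corr(B, C). Take ρ = 0.6 and suppose that a high screening level goes with worse outcome (β_B = −0.5) while a fall goes with better outcome (β_C = −0.224). Then corr(Y, C) = −0.224 + (−0.5)(−0.447) = 0. A real on-treatment relation disappears from the unadjusted analysis.

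**5. What baseline markers could show.** Expected responders are 25 × 0.05 = 1.25 to 25 × 0.25 = 6.25.
- If 12 patients are classed high and 13 low, the smallest Fisher p is 12/25 = 0.48 with one responder and (12 × 11)/(25 × 24) = 0.22 with two.
- With 6 responders and 19 non-responders, Wilcoxon power is 0.33, 0.47 and 0.82 for standardised differences of 0.8, 1.0 and 1.5.

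These analyses can describe; they cannot confirm.

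**The case against.** The case against has several parts.

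- **The hypothesis is about mechanism.** Section 1.2.1 expects benefit through suppression of inflammation, and change against response is the direct counterpart of that idea. This stands as a reason to keep the change analysis. It does not justify leaving it unadjusted, because the mechanism question is whether change matters for a given starting level.
- **Baseline markers are not excluded.** A reader might infer that baseline pathway or inflammatory activity is never tested. The documents do not support that. The general univariate clause in section 7.2.1 could take in screening cytokines or the differential, the later SAP could name them, and tissue JAK1 mutation is itself a baseline marker. What is missing is a prespecified analysis: the clause names no marker and no outcome.
- **JAK1 mutation.** A reader might call it off target because section 1.2.1 does not list it. The sentence there, "The persistent or constitutive phosphorylation of STAT3 in cancers may occur via a variety of mechanisms, including increased expression of cytokines and cytokine receptors", introduces examples and is not exhaustive. JAK1 mutation measures genotype and not activity, but it is a legitimate marker.
- **Power.** It is tempting to say that a baseline analysis has 73% power and a change analysis 12% to 26%. That comparison assumes that baseline is the true predictor. If change were the true predictor, the figures would swap. It is not evidence of harm.
- **Single arm.** A baseline association could be purely prognostic, and titles in the protocol's reference list already describe the neutrophil-lymphocyte ratio as prognostic in HCC. This stands in full and limits what may be claimed.

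**Conclusion.** The point holds as a low-severity improvement. Section 2.3 plans a cytokine-change analysis without saying that it is adjusted for the screening value, and it prespecifies no analysis of screening inflammatory level against outcome, in a study aimed at inflammatory HCC that does not select for it.

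Under the assumptions listed, the unadjusted analysis would produce a significant but misleading association in roughly 12% to 28% of trials, against about 5% when adjusted. With other coefficients it would hide a real one. These sizes depend on the assumed r = 0.5, on ρ between 0.4 and 0.8 and on a continuous outcome; the algebraic link between change and baseline does not depend on r.

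A reader might infer that the trial thereby fails to test its rationale and that the additions would cure this. Neither follows: with one arm and about 1 to 6 responders, no biomarker analysis here can show that inflammatory HCC benefits more from the drug. Primary and secondary endpoints are unaffected.

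**What to change.** Amend sections 2.3 and 7.2.1, or put the following in the separate SAP before database lock.

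1. Analyse cytokine change against response with adjustment for the screening value. With so few responders, a linear model of change on screening value and response group is likely to be more stable than a logistic model with two covariates.
2. Name as exploratory baseline markers the screening cytokine levels, with IL-6 first because section 1.2.1 names it, and the screening neutrophil-lymphocyte ratio. Report each against week-8 response and PFS with 95% confidence intervals.
3. Label these results hypothesis-generating, without multiplicity control, and as associations that a single arm cannot separate into prognostic and predictive effects.

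**Cost.** Wording and a few extra table rows. Table 1 already provides the screening differential and research bloods. It does not itemise the research bloods, but a change score needs a pre-treatment cytokine value and screening is the only pre-treatment research sample marked. No sample, visit or assay is added; in particular, a phospho-STAT3 stain is not needed. Sample size, stopping rule and power stay as stated. The downside is a few more imprecise estimates, which the labelling in item 3 covers.

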1.2.2 Pre-Clinical Studies

1.2.2.1 In Vitro Studies

The selective inhibition of JAK1 compared to JAK2 by Itacitinib has been demonstrated in biochemical assays; with additional analyses performed using cell-based assays known to signal through JAK2 homodimer (Murray 2007).

Effects of pathogenesis of RA, such as IL-2 stimulated phosphorylation of JAKs and STATs and IL-2- induced proliferation of cells; as well as the inhibition of phosphorylation of STAT proteins and the production of proinflammatory factors (eg, IL-17, MCP-1) induced by other cytokines, such as IL-23 and IL-6 have also been seen with ICNB039110.

Analysis of human INA-6 multiple myeloma cell line determined the ability of Itacitinib to inhibit cell growth by the inactivation of JAK/STAT3 through the withdrawal of IL-6 or inhibition of IL-6 binding to the IL-6 receptor which induces cell death via apoptosis (Burger et al 2001).

Whole blood assays were used to estimate the effectiveness of blocking JAK in hematopoietic cells *in vivo*, results showed Itacitinib blocked IL-6- induced STAT3 phosphorylation in human whole blood, whereas the potency of Itacitinib in blocking TPO-induced pSTAT3 was significantly reduced, consistent with the JAK1 selectivity measured in the biochemical assays.

Further details can be found in the investigator brochure.

1.2.2.2 Pre-Clinical Toxicology

The toxicology profile of Itacitinib was characterized in single- and multiple-dose oral studies, of up to 6 months in duration in rats and 9 months dogs, and in genetic, photo toxicity, and embryo-fetal developmental toxicology studies.

Single oral doses of Itacitinib up to 2000 mg/kg in rats produced no adverse effects. In multiple-dose studies in rats, dose-related body weight decreases and lower food consumption were noted. Pharmacology-related clinical pathology and anatomical alterations in multiple-dose rat studies included a reversible lowering of white blood cell (WBC) count, primarily because of a lower circulating lymphocyte count, a reversible lymphoid depletion in lymphoid tissues, and a reduction in bone marrow cellularity. The NOAEL in the 6-month rat study was determined to be 300 mg/kg per day for both males and females.

Single oral doses of Itacitinib of up to 1000 mg/kg in dogs produced no adverse effects. In multiple-dose studies in dogs, gastrointestinal (GI) inflammation was determined to be the dose-limiting toxicity (DLT) in studies of up to 3 months in duration. In the 6- and 9-month studies, generalized demodicosis, an effect secondary to the immunosuppressive effect of Itacitinib, was the DLT. The NOAEL in the 9-month study was determined to be 10 mg/kg per day.

Itacitinib was not genotoxic in the bacterial mutagenicity assay, the *in vitro* chromosome aberration assay in human lymphocytes, or the *in vivo* micronucleus assay in rats. Itacitinib did not demonstrate phototoxic potential in the *in vitro* neutral red uptake photo toxicity study.

When administered to pregnant rats and rabbits, Itacitinib caused fetotoxicity and fetal malformations and variations only at the highest doses tested. In the rat, all fetal effects were considered secondary to Itacitinib administration because of severe maternal toxicity observed at the same dose level as the fetotoxicity.

Further details can be found in the investigator brochure.

1.2.3 Clinical Studies

As of the data cutoff date (30 APR 2021), 34 clinical studies with itacitinib (18 Phase 1, 7 Phase 1/2, 7 Phase 2, and 2 Phase 3), including studies of itacitinib as monotherapy and in combination with chemotherapeutic agents, corticosteroids, CNI-based interventions, pembrolizumab (anti-PD-1 monoclonal antibody), tyrosine kinase inhibitors (ibrutinib and osimertinib, investigational PI3Kδ (INCB040093 and pascalisib), a JAK inhibitor (ruxolitinib), and an IDO1 (epacadostat) inhibitor, have either been completed or are ongoing.. In addition, a rollover study has been initiated for participants who were continuing to receive benefit from treatment with itacitinib at the time of their study's closure. As of the cutoff date, approximately 1699 unique participants, which includes 543 healthy adult participants, have been exposed to itacitinib..Phase 1 included 11 completed studies.

- **INCB 39110-101** was a Phase 1, double-blind, randomized, placebo-controlled, single-dose escalation study to assess the safety, tolerability, and PK of Itacitinib when administered orally to healthy adult subjects. This study was conducted in 3 cohorts of up to 12 subjects each. Cohort 1 received single doses of 10 mg, 50 mg, 200 mg, and 500 mg with at least 2 weeks between doses. Cohort 2 received single doses of 20 mg, 100 mg, and 300 mg with at least 2 weeks between doses. Cohort 3 received a single dose of 1000 mg.
- **INCB 39110-102** was a Phase 1, relative bioavailability study of 4 Itacitinib SR formulations compared with the IR formulation, and evaluated the effect of food on the SR formulations in healthy adult subjects. This study employed a 3-period crossover design with subjects randomized to various sequences of SR

fasted, SR fed (after a standardized high-fat meal), and IR fasted with 1 week between doses. Five cohorts of 12 subjects were evaluated with single 300 mg doses of IR, SR1, SR2, SR3, and SR4 formulations. Also, 6 subjects in Cohort 1 were evaluated with a microdose of ¹⁴C-Itacitinib (700 nCi/0.008 mg) in 50 mg liquid with 250 mg in tablets in a fourth study period. Cohort 6 evaluated doses of 50 mg Itacitinib SR3 (administered as two 25 mg tablets) and 100 mg SR3 (one 100 mg tablet) in the fed and/or fasted states in 12 additional healthy adult subjects.

- **INCB 39110-103** was a Phase 1, double-blind, randomized, placebo-controlled, multiple-dose escalation study to assess safety, tolerability, and PK of Itacitinib when administered orally to healthy adult subjects. Five cohorts of up to 12 subjects completed dose administration of Itacitinib SR1 200 mg BID, 400 mg BID, and 600 mg BID in the fasted state and 400 mg and 600 mg BID in the fed state (medium-fat meal). Two cohorts of up to 12 subjects completed dose administration of doses of Itacitinib SR3 400 mg BID and 800 mg QD in the fed state (medium-fat meal).
- **INCB 39110-105** Open-label, randomized, crossover, Phase 1 study, to assess Relative bioavailability of IR and SR tablets and food effect. Itacitinib 200, 300, or 600 mg SR or IR PO after fast of ≥ 10 hours, after a high-fat meal, or after a medium-fat meal. 129 healthy adult participants
- **INCB 39110-109** Open-label single-centre Phase 1 study to assess PK-mass balance and metabolite profile, Itacitinib 300 mg SR PO + 100 mL [¹⁴C] Itacitinib adipate 500 μ Ci (~4.9 mg). 7 Healthy participants aged 18 to 55 years
- **INCB 39110-111** Open label, phase 1 trial of 42 healthy participants 18-55 yrs old to Compare relative bioavailability of Itacitinib 200 mg SR tablets (test) with Itacitinib 2 \times 100 mg SR tablets
- **INCB 39110-115** was a Phase 1, double-blind, randomized, placebo-controlled, multiple-dose study to assess the effect of Itacitinib on renal function in healthy adult subjects. Twenty-four subjects were enrolled to receive Itacitinib SR3 600 mg BID and corresponding placebo for 8 days in a 2-period crossover design.
- **INCB 39110-122** open label, phase 1 trial to assess the effect of renal dysfunction on itacitinib PK (C_{max} and AUC_{0- ∞}) 300 mg itacitinib single dose PO following a medium-fat meal of 26 healthy healthy participants and participants with renal impairment or ESRD

Eight studies (INCB 39110-101, -102, -103, 113, 116, 118, 122 and 123) explored the PK, safety, and preliminary pharmacology of Itacitinib and contribute to the safety and clinical pharmacology data. The fourth study (INCB 39110-115) was completed in healthy adult subjects to assess the effects of Itacitinib on renal function. In completed clinical pharmacology studies, Itacitinib has been administered to 188 healthy adult subjects as a single dose, repeat single doses, or multiple doses for up to 10 days.

It was noted during the Phase 1 studies, which compared SR formulations, that the SR3 formulation exhibited the highest relative bioavailability compared with the IR formulation, and the least significant food-effect as measured by total mean exposure. Therefore, the 100 mg Itacitinib SR3 tablet formulation was selected for use in the Phases 1b and Phase 2 studies (noted as SR for these studies).

The Phase 2 program includes 2 completed proof-of-concept studies in subjects with active RA (INCB 39110-201) and psoriasis (INCB 39110-250) as well as 5 on-going clinical trials.

- **INCB 39110-201** was a Phase 2, double-blind, placebo-controlled, 2-part study of Itacitinib administered orally to subjects with active RA. In Part 1, a 28-day course of Itacitinib or corresponding placebo was administered orally to 3 staggered cohorts of 10 to 15 subjects each in doses of 400 mg BID, 100 mg BID,

and 100 mg QD. In Part 2, 28 days of oral administration were followed by an additional 56-day course of placebo or Itacitinib at the originally randomized dose, without regard to food.

- **INCB 39110-250** was a Phase 2a, double-blind, placebo-controlled, 28-day study of Itacitinib administered orally to subjects with stable, chronic plaque psoriasis. Itacitinib SR 100 mg tablets or corresponding placebo were administered orally as 100 mg QD, 200 mg QD, 200 mg BID, and 600 mg QD either 30 minutes before or 2 hours after a meal.

As of 30 APR 2021, 1699 unique study participants have been exposed to itacitinib, as follows:

- Healthy participants (543 participants)
- Itacitinib monotherapy (278 participants)

Adverse events that have been reported as very common ($\geq 1/10$) in healthy participants include headache and common ($\geq 1/100$ to $< 1/10$) neutropenia. In patients with underlying disease receiving monotherapy treatment, very common adverse reactions include anemia, pyrexia and headache. Adverse events reported by more than 10% of subjects receiving Itacitinib in the psoriasis study included nasopharyngitis.

Adverse events reported by more than 10% of subjects in the MF study included anaemia, fatigue, thrombocytopenia/platelet count decreased, nausea, diarrhoea, upper respiratory tract infection, constipation, cough, dyspnoea, peripheral oedema, pyrexia, dizziness, abdominal pain, night sweats, pain in extremity, arthralgia, contusion, headache, pruritus, vomiting, and increased bilirubin/hyperbilirubinemia. In the RA study, there were no TEAEs reported by more than 10% of subjects.

Events reported in $> 20\%$ of subjects in Study INCB 39110-116 and Study INCB 39110-203 in which Itacitinib was given in conjunction with chemotherapy were as follows: fatigue, anaemia, thrombocytopenia/platelet count, nausea, neutropenia/febrile neutropenia/neutrophil count decreased and agranulocytosis, pyrexia, diarrhoea, peripheral oedema, dysgeusia, headache, peripheral neuropathy, alopecia, cough, decreased appetite, dyspnoea, constipation, and dehydration. In lymphoid malignancies where Itacitinib was given in combination with INCB040093 or INCB050465, PI3K δ inhibitors, TEAEs observed in $\geq 10\%$ of subjects in Study INCB 40093-102 and Study INCB 40093-201 included nausea, cough, diarrhoea, thrombocytopenia/platelet count decreased, vomiting, pyrexia, fatigue, chills, night sweats, aspartate aminotransferase increased, neutropenia/neutrophil count decreased, constipation, decreased appetite, headache, back pain, dyspnoea, oropharyngeal pain, alanine aminotransferase increased, abdominal pain, anaemia, upper respiratory tract infection, asthenia, peripheral oedema, blood cholesterol increased, dizziness, muscle spasms, pain in extremity, rash, pruritus, tachycardia, blood creatinine increased, stomatitis, bronchitis, herpes zoster, sinusitis, hyponatremia, anxiety, dyspnoea exertional, hypotension, hypoxia, and urinary tract infection. Serious adverse events reported in more than 1 subject where Itacitinib was given in combination with INCB040093 included PCP (5 subjects), pyrexia (5 subjects), pneumonia (4 subjects), urinary tract infection (3 subjects), hypoxia (3 subjects), cardiac arrest (2 subjects), colitis (2 subjects), herpes zoster (2 subjects), respiratory failure (2 subjects), and syncope (2 subjects). For this combination treatment, certain classes of events are notable.

- **Infection:** Adverse events classified as infections occurred in 59.3% of subjects. Infections reported in more than 3 subjects included upper respiratory infection (14.8%), PCP (9.3%), urinary tract infection (9.3%), bronchitis (7.4%), fungal infection (7.4%), herpes zoster (7.4%), oral herpes (7.4%), and pneumonia (7.4%). Because of the increased risk of PCP in subjects receiving Itacitinib in combination with INCB040093, a standard prophylaxis regimen is now required for all subjects receiving this

combination. Since implementing this requirement, no additional cases of PCP have been observed in subjects receiving prophylaxis.

- Myelosuppression: Anaemia was observed in 14.8% of subjects, neutropenia was observed in 27.8% of subjects, and thrombocytopenia was observed in 33.3% of subjects.
- Hyperlipidaemia: Hyperlipidaemia has previously been noted in subjects receiving JAK inhibitors (Kontzias et al 2012). Six subjects (11.1%) were observed to have an increase in blood cholesterol that was greater than the upper limit of normal after receiving combination treatment with Itacitinib and INCB040093.

Serious AEs have been reported in RA (2 subjects), MF (28 subjects), solid tumours (25 subjects), and lymphoid malignancies (22 subjects). Itacitinib Investigator's Brochure v9_06FEB2017

Serious AEs reported in more than 1 subject in an individual study included the following:

- Pneumonia/bacterial pneumonia (3 MF subjects receiving monotherapy, 7 subjects receiving Itacitinib in combination with chemotherapy, and 3 subjects receiving Itacitinib in combination with INCB040093)
- *Pneumocystis jirovecii* pneumonia (5 subjects receiving Itacitinib in combination with INCB040093)
- Anaemia (5 MF subjects receiving monotherapy and 5 subjects receiving Itacitinib in combination with chemotherapy)
- Pyrexia (2 MF subjects receiving monotherapy, 2 subjects receiving Itacitinib in combination with chemotherapy, and 4 subjects receiving Itacitinib in combination with INCB040093)
- Congestive cardiac failure (3 MF subjects receiving Itacitinib monotherapy, 1 subject receiving Itacitinib in combination with chemotherapy)
- Chest pain (2 MF subjects receiving Itacitinib monotherapy)
- Acute renal failure (2 MF subjects receiving Itacitinib monotherapy, 1 subject receiving Itacitinib in combination with chemotherapy)
- Urinary tract infection (2 MF subjects receiving Itacitinib monotherapy, 1 subject receiving Itacitinib in combination with chemotherapy, 2 subjects receiving Itacitinib in combination with INCB040093)
- Respiratory failure (including acute and hypoxic respiratory failure) (3 subjects receiving Itacitinib in combination with chemotherapy, 2 subject receiving Itacitinib in combination with INCB040093)
- Gastrointestinal/upper gastrointestinal haemorrhage (2 MF subject receiving Itacitinib monotherapy, 3 subjects receiving Itacitinib in combination with chemotherapy)
- Febrile neutropenia (2 subjects receiving Itacitinib in combination with chemotherapy)

As a result of Itacitinib-mediated immunomodulation, whether administered alone or in combination with another agent, an increased incidence of infections could possibly occur. Strict clinical monitoring is indicated to identify and treat infections in study subjects should they occur. Because of the potential for myelosuppression, subjects should have hematologic parameters closely monitored during initial clinical studies. If there are clinically relevant declines in haematology parameters, therapy may be interrupted until resolution or discontinuation. Dose-escalation criteria regarding changes in haematological parameters should be specified in individual protocols. As Itacitinib also has the potential to cause WBC margination (ie, a transient decrease in ANC), assessment of haematology parameters should be performed before study drug administration at all applicable study visits.

Further details can be found in the investigator brochure.

